Ascertainment bias will be assessed by analyzing the site Investigator data. The stratified log-rank test will be repeated on PFS using the site Investigator data based on RECIST. Disagreements between Investigator and central reviews of RECIST progression will be presented for each treatment group.

The assumption of proportionality will be assessed firstly by examining plots of complementary log-log (event times) versus log (time) and, if these raise concerns, by fitting a time-dependent covariate to assess the extent to which this represents random variation. If a lack of proportionality is evident, the variation in treatment effect will be described by presenting piecewise HR calculated over distinct time-periods. In such circumstances, the HR can still be meaningfully interpreted as an average HR over time unless there is extensive crossing of the survival curves. If lack of proportionality is found, this may be a result of treatment-by-covariate interactions, which will be investigated. In addition, the Kaplan-Meier curve along with landmark analyses (eg, 1-year PFS rate) will also help in understanding the treatment benefit.

Subgroup analyses will be conducted comparing PFS (per RECIST 1.1 using BICR assessments) between durvalumab monotherapy and durvalumab and tremelimumab combination therapy versus placebo in the following subgroups of the FAS (but not limited to):

- TNM stage (Stage I/II versus III)
- Receipt of PCI (yes versus no)
- Time from end date of cCRT to randomization in this study (<14 days, ≥14 to <28 days, ≥28 days)
- Time from last dose of radiotherapy to randomization in this study (<28 days,  $\ge28$  to <56 days,  $\ge56$  to <84 days,  $\ge84$  days)
- Prior platinum chemotherapy (carboplatin versus cisplatin)
- Prior radiotherapy regimen (daily versus twice daily)
- Best response to CRT (CR versus PR versus SD)
- Sex (male versus female)
- Age (<65 versus  $\ge 65$  years of age)
- PD-L1 status (< 1% versus  $\ge 1\%$ )
- Smoking status (smoker versus non-smoker [never smoker])
- Race/ethnicity

- Geographic region
- WHO/ECOG PS (0 versus 1)

Other baseline variables may also be assessed if there is clinical justification or an imbalance is observed between the treatment groups. The purpose of the subgroup analyses is to assess the consistency of treatment effect across expected prognostic and/or predictive factors. Forest plot(s) will be generated.

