1.3 Number of Subjects

The study will plan to enroll approximately 965 patients globally in order to randomize approximately 724 patients to 1 of 3 treatment groups: durvalumab monotherapy (approximately 262 patients), placebo (approximately 262 patients), or durvalumab + tremelimumab combination therapy (approximately 200 patients) over a period of approximately 38 months. Initially, patients will be randomized 1:1:1 to the 3 treatment groups. Following implementation of CSP Version 4, once 600 patients have been randomized, a further 124 patients will subsequently be randomized 1:1 to durvalumab monotherapy or placebo until a total of approximately 724 patients have been randomized.

The study has dual primary objectives which are to assess the efficacy of durvalumab monotherapy compared to placebo in terms of PFS per RECIST 1.1 as assessed by BICR, and OS.

The primary PFS analysis will occur at the earliest of:

- 1. When approximately 370 PFS BICR events have occurred (70.6% maturity) in the durvalumab monotherapy and placebo treatment groups
- 2. At OS-IA2, if OS-IA2 is statistically significant (durvalumab monotherapy vs placebo)
- 3. Approximately 36 months after the last patient randomized

If the true PFS HR is 0.65 for durvalumab monotherapy versus placebo, with 370 PFS BICR events, the study will have approximately 90% power to demonstrate a statistically significant difference in PFS between durvalumab monotherapy and placebo, with an overall 2-sided significance level of 0.5%. The true HR of 0.65 translates to a 5.4 month benefit in median PFS over 10 months on placebo if PFS is exponentially distributed. The smallest treatment difference that would be statistically significant is a HR of 0.743 (Critical value (CV)). At this time, approximately 309 PFS BICR events are also expected to have occurred in the durvalumab in combination with tremelimumab and placebo treatment groups. A recruitment period of approximately 38 months was assumed in the CSP for the primary PFS analysis.

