3. PRIMARY AND SECONDARY VARIABLES

3.1 Derivation of RECIST Visit Responses

For all patients, the RECIST tumor response data will be used to determine each patient's visit response according to RECIST version 1.1 (see further Appendix F of the CSP). It will also be used to determine if and when a patient has progressed in accordance with RECIST and their best objective response to study treatment.

Baseline radiological tumor assessments are to be performed post-cCRT within the 42 days before randomization and start of study treatment. Tumor assessments are then performed every 8 weeks (\pm 1 week) for the first 72 weeks (relative to the date of randomization), followed by every 12 weeks (\pm 1 week) up to 96 weeks (relative to the date of randomization), and then every 24 weeks (\pm 1 week) thereafter (relative to the date of randomization) until RECIST 1.1-defined radiological progression, plus one follow-up scan no earlier than 4 weeks later and no later than the next regularly scheduled imaging visit.

If an unscheduled assessment is performed, and the patient has not progressed, every attempt should be made to perform the subsequent assessments at their scheduled visits. This schedule is to be followed to minimize any unintentional bias caused by some patients being assessed at a different frequency than other patients.

From the investigator's review of the imaging scans, the RECIST tumor response data will be used to determine each patient's visit response according to RECIST version 1.1. At each visit, patients will be programmatically assigned a RECIST 1.1 visit response of CR, PR, SD or Progressive disease (PD), using the information from target lesions (TLs), non-target lesions (NTLs) and new lesions and depending on the status of their disease compared with baseline and previous assessments. If a patient has no evidence of disease (NED) at baseline, then the patient will be assigned a visit response of NED if there is still no evidence of disease or PD if there is evidence of progression. If a patient has had a tumor assessment which cannot be evaluated, then the patient will be assigned a visit response of not evaluable (NE) (unless there is evidence of progression in which case the response will be assigned as PD).

RECIST outcomes (i.e. PFS and ORR etc.) will be calculated programmatically for the BICR and site investigator data from overall visit responses.

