4. ANALYSIS METHODS

4.1 General Principles

All summaries will be presented in tabular format by treatment group, unless otherwise specified. Data will be presented in data listings by treatment group and patient number.

A month is operationally defined to be 30.4375 days. Six months is operationally defined to be 183 days.

The below mentioned general principles will be followed throughout the study:

- Descriptive statistics will be used for all variables, as appropriate. Continuous
 variables will be summarized by the number of observations, mean, standard
 deviation, median, upper and lower quartiles minimum, and maximum. For log
 transformed data it is more appropriate to present geometric mean, coefficient of
 variation, median, minimum and maximum. Categorical variables will be summarized
 by frequency counts and percentages for each category.
- Unless otherwise stated, percentages will be calculated out of the population total and for each treatment group.
- For continuous data, the mean and median will be rounded to 1 additional decimal place compared to the original data. The standard deviation will be rounded to 2

additional decimal places compared to the original data. Minimum and maximum will be displayed with the same accuracy as the original data.

- For categorical data, percentages will be rounded to 1 decimal place.
- P-values will be rounded to 4 decimal places (with the exception of those in the MTP). P-values less than 0.00005 (e.g. 0.00002) will not be rounded to 4 decimal places (e.g. 0.0000) but instead be displayed as <0.0001. P-values output as <0.0001 by statistical software will not be rounded and will be displayed in the same way ('<0.0001'). P-value presented for the MTP will be rounded to 5 decimal places.
- SAS® version 9.4 will be used for all analyses.

Efficacy and PRO data will be summarized and analyzed on the FAS, or combination analysis set where stated. Safety and treatment exposure data will be summarized based on the safety analysis set, or combination safety analysis set where stated. Study population and demography data will be summarized based on the FAS, or combination analysis set where stated.

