If non-proportional hazards are observed, this may be investigated further. Under nonproportional hazards, the HR from the primary analysis can still be meaningfully interpreted as an average HR over time unless there is extensive crossing of the survival curves. However, under non-proportional hazards the variation in treatment effect may be described by presenting piecewise HR calculated over distinct time-periods: 0-6m, 6-12m, 18-24m, >24m, using a Cox regression model with time-dependent covariates, stratified by the same factors as the primary analysis. Under non-proportional hazards, the Restricted Mean Survival Time (RMST) may also be analysed up to the minimum of the largest observed event time in each of the two arms, using the pseudovalues approach (Andersen et al. 2004) an areaunder-the-curve approach (Kaplan-Meier method), with standard error, for each treatment group, along with the estimate of difference in means (and ratio of means) between treatment groups, with 95% confidence intervals and p-value. The standard error of the difference will be estimated using Generalised Estimating Equations (PROC GENMOD, Klein et al. 2008), with covariate adjustment for stratification factors. The standard error for the RMST ratio (unadjusted) may be estimated from the treatment group RMSTs using the delta method. In addition, an area-under-the-curve approach (Kaplan-Meier method) the pseudovalues approach (Andersen et al. 2004) and Royston-Parmar model (Royston and Parmar 2011, 2013) may also be used; all RMST analyses [except RMST ratio] will control for the stratification factors used in the primary analysis. Additional analyses such as the MaxCombo test may also be performed.

The treatment status at progression of patients at the time of analysis will be summarized. This will include the number (%) of patients who were on treatment at the time of progression, the number (%) of patients who discontinued study treatment prior to progression, the number (%) of patients who have not progressed and were on treatment or discontinued treatment. This will also provide distribution of number of days prior to progression for the patients who have discontinued treatment.

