4.2.3 Overall survival

The primary analysis of OS in the FAS will be analyzed using stratified log-rank tests using the same methodology as described for the PFS endpoint.

The treatment effect will be estimated by the HR together with its corresponding CI (95% and $[1-adjusted\ alpha] \times 100\%$) from a stratified Cox proportional hazards model.

Kaplan-Meier plots of OS will be presented by treatment group. Summaries of the number and percentage of patients who have died, those still in survival follow-up, those lost to follow-up and those who have withdrawn consent will be provided along with the median OS together with its corresponding 95% CI for each treatment group. The CI for median overall survival will be derived based on Brookmeyer-Crowley method with log-log transformation (SAS Institute Inc. 2018).

The assumption of proportionality will be assessed in the same way as for PFS.

Sensitivity analysis

A sensitivity analysis for OS will examine the censoring patterns to rule out attrition bias with regards to the treatment comparison of primary analysis, achieved by a Kaplan-Meier plot of time to censoring where the censoring indicator of OS is reversed.

The number of patients prematurely censored will be summarized by treatment group. A patient would be defined as prematurely censored if their survival status was not defined at the DCO.

In addition, duration of follow-up will be summarized using medians (as well as minimum and maximum):

- Time from randomization to the date of death (i.e. overall survival) or to the date of censoring (date last known to be alive, for censored patients) summarized in all patients regardless of treatment arm, as well as by treatment arm.
- Time from randomization to the date of censoring in censoring patients only, presented by treatment arm.

Duration of OS follow-up will also be summarized using median (and interquartile range), estimated by analyzing time to censoring with the reverse Kaplan-Meier method (i.e. OS censoring and event flags reversed), presented by treatment arm and overall.

Subgroup analyses and a forest plot will be generated comparing OS between treatments of primary analysis in the same way as previously specified for PFS.

No adjustment to the significance level for testing will be made since all these subgroup analyses will be considered supportive of the primary analysis of OS.

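### The SAP's periods for piecewise hazard ratios skip months 12 to 18, so a supportive, conditional analysis has no labelled estimate for that band

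*SAP*

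**What the plan says.** SAP section 4.2.2, under its supportive summaries for PFS, states that "under non-proportional hazards the variation in treatment effect may be described by presenting piecewise HR" and fixes the periods: "piecewise HR calculated over distinct time-periods: 0-6m, 6-12m, 18-24m, >24m". The estimates are to come from one model, "using a Cox regression model with time-dependent covariates, stratified by the same factors as the primary analysis".

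Protocol section 9.5.1.1 makes the same analysis firmer: if non-proportionality is evident, "the variation in treatment effect will be described by presenting piecewise HR calculated over distinct time-periods". It names no periods, so the SAP sentence is their only definition. SAP section 6, which lists changes from the protocol, says nothing about leaving out a period.

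For OS, SAP section 4.2.3 says only this: "The assumption of proportionality will be assessed in the same way as for PFS". Using the same periods for OS is therefore implied but not stated.

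**The concern.** The list runs in six-month steps, skips one step, then resumes and ends with an open period. It looks like a drafting slip, but as written it is the pre-specified rule.

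Two things are at stake. First, the purpose of the analysis is to show how the treatment effect varies over follow-up, and a reader would find no estimate for six months in the middle of it. That band lies inside the treatment period, which lasts up to 24 months. Second, patients at risk in months 12 to 18 stay in the single Cox model, and the SAP does not say how treatment enters there. Two programmers could follow the text and produce different fits. Adding the period later would be an unplanned choice of cut-points, made after the data had already shown non-proportional hazards.

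**Working it through.** **Coverage.** The listed periods cover 0 to 12 months and everything after 18 months. The uncovered band is 12 to 18 months.

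**Scans in the gap.** SAP section 3.1: "Tumor assessments are then performed every 8 weeks", up to week 72 from randomization. SAP section 4.1: "A month is operationally defined to be 30.4375 days". The band therefore runs from 12 × 30.4375 = 365.25 days to 18 × 30.4375 = 547.9 days. The scheduled scans inside it are:

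- week 56: 392 / 30.4375 = month 12.9
- week 64: 448 / 30.4375 = month 14.7
- week 72: 504 / 30.4375 = month 16.6

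**What the model does in the gap.** In a Cox model whose only covariate is treatment by period, each event's partial-likelihood term involves only the coefficient active at that event time.

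- *Four listed terms, no treatment main effect.* The coefficient in months 12 to 18 is zero, so the hazard ratio there is exp(0) = 1 by construction.
- *Main effect plus four terms.* Months 12 to 18 become the reference. The main effect is the log hazard ratio for that band, but no listed period carries the label.

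A check on one simulated data set (1,500 per arm, true hazard ratio 1 to month 6 and 0.5 after) gave:

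| Coding | 0-6 | 6-12 | 12-18 | 18-24 | >24 |
|---|---|---|---|---|---|
| Five periods | 1.063 | 0.426 | 0.545 | 0.390 | 0.542 |
| Four terms only | 1.063 | 0.426 | 1.000 (fixed) | 0.390 | 0.542 |
| Main effect + four terms | 1.063 | 0.426 | 0.545 | 0.390 | 0.542 |

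Only the months 12 to 18 value depends on the coding.

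**Events in the gap: inputs.** SAP section 1.3: "If the true PFS HR is 0.65 for durvalumab monotherapy versus placebo, with 370 PFS BICR events", placebo median 10 months, exponential times, 262 patients per arm, recruitment over about 38 months. Added assumptions: uniform accrual and no dropout.

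*Reproducing the plan's figure.* Power = Φ(|ln 0.65| × √370 / 2 − z) with z = 2.807 for 2-sided 0.5%: Φ(0.4308 × 9.618 − 2.807) = Φ(1.336) = 0.909. At the primary-analysis level of 0.444% it is 0.903. The SAP states approximately 90%, so the inputs are read correctly.

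*Without administrative censoring.* λ0 = ln 2 / 10 = 0.0693 and λ1 = 0.65 × λ0 = 0.0451. The probability of an event in months 12 to 18 is exp(−12λ) − exp(−18λ): 0.1481 on placebo and 0.1379 on durvalumab. Expected events: 262 × (0.1481 + 0.1379) = 74.9.

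*With administrative censoring.* For entry time u uniform on 0 to 38, cut-off T and follow-up f = T − u, the expected events in (a, b] are the sum over arms of 262 × mean over u of [exp(−λ min(a, f)) − exp(−λ min(b, f))]. T is chosen so that all events sum to the target.

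| Analysis | T (months) | 0-6 | 6-12 | 12-18 | 18-24 | >24 | Share in 12-18 |
|---|---|---|---|---|---|---|---|
| PFS, 308 events | 38.1 | 140.5 | 81.9 | 46.0 | 24.2 | 15.3 | 14.9% |
| PFS, 370 events | 44.3 | 151.2 | 99.1 | 58.1 | 32.9 | 28.7 | 15.7% |
| OS, 348 deaths (median 24 months, HR 0.73) | 64.8 | 72.8 | 62.5 | 53.6 | 46.1 | 113.0 | 15.4% |

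*Sensitivity.* With 0 to 10% annual dropout and accrual over 30 to 38 months, the share is 15.7 to 17.0% for PFS at 370 events and 13.5 to 15.4% for OS at 348 deaths.

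The analysis is triggered only by non-proportional hazards, so such patterns were simulated for PFS (400 replicates each, placebo median 10 months, 370 events). Events in months 12 to 18:

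| Assumed hazard ratio | Events | Share of 370 |
|---|---|---|
| 1 to month 12, then 0.5 | 44.2 | 11.9% |
| 1 to month 6, then 0.5 | 50.0 | 13.5% |
| 0.5 to month 18, then 1 | 55.9 | 15.1% |
| 0.5 to month 12, then 0.8 | 68.5 | 18.5% |

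*Limit of the projection.* At 308 PFS events the model gives about 186 deaths, against the 242 anticipated in SAP section 5.1.

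**The case against.** The strongest reply is that this is an obvious slip in an optional analysis. The SAP wording is permissive, the analysis is reached only if the log-log plots and then a time-dependent covariate raise concern, it carries no alpha, and anyone can see which band was intended. The period is not hidden either: the Kaplan-Meier curves, a one-year PFS rate and PFS18 bracket it, and RMST uses the same data. With a main effect in the model, the months 12 to 18 hazard ratio is in fact estimated, as the reference term. All of this stands and holds the point at minor. It does not remove it, because the only written definition of the periods still omits one and no listed period would carry its estimate.

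The event counts can also be challenged. Besides the shortfall in deaths, the model reaches 308 PFS events about 38 months after first entry. The protocol estimated first enrollment in Q3 2018, yet its version 5.0 of January 2023 introduced the 308-event interim as a future analysis. That criticism is fair. The counts show only that the band is unlikely to be empty.

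Finally, carrying the periods over to OS is an inference from SAP section 4.2.3, and once all five periods are present, equivalent codings give the same hazard ratios. Both points are correct, so the coding and OS statements in the remedy are clarifications, not corrections of error.

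**Conclusion.** The concern holds, as a minor defect. SAP section 4.2.2 lists periods that do not cover follow-up, and neither document fills or explains the gap at months 12 to 18. Followed exactly, the analysis gives no labelled treatment effect there, and the fitted value in the band is left to unspecified coding.

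Under the design assumptions with uniform accrual and no dropout, the band would hold about 58 of 370 PFS events. Across the non-proportional patterns tried, it would hold 44 to 69. If the same periods were used for OS, it would hold about 54 of 348 deaths. These are illustrations from a model that does not match the plan's own event forecast, and the conclusion does not rest on them.

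The other four period estimates and the study's alpha, power and sample size are unaffected, as are the log-rank tests, overall hazard ratios, Kaplan-Meier curves, PFS18, PFS24 and RMST.

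**What to change.** In SAP section 4.2.2, replace the list with contiguous periods: 0-6, >6-12, >12-18, >18-24 and >24 months. Say that they cover all follow-up and that one treatment-by-period term is fitted per period with no separate treatment main effect. In the same place, state whether these periods also apply to OS; using the same ones is the simplest choice. The cost is one SAP line. No other planned analysis changes.

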# 9.5.1.1 Progression-free survival

The primary PFS analysis will be based on the programmatically derived RECIST 1.1 using BICR tumor assessments. The analysis will be performed in the FAS using a stratified log-rank test adjusting for TNM stage (I/II versus III) and receipt of PCI (yes versus no). The effect of durvalumab monotherapy and durvalumab and tremelimumab combination therapy versus placebo treatment will be estimated by the hazard ratio (HR) together with its corresponding confidence interval (CI) (95% and [1-adjusted alpha] × 100%) from a stratified Cox proportional hazards model.

In order to ensure there are at least 5 events within each strata; if there are too few events in the Stage I/II stratification level, TNM stage may be excluded from the models leaving receipt of PCI as the sole stratification factor.

Secondary PFS analyses will be performed using the same methodology as for the primary analysis.

Kaplan-Meier plots of PFS will be presented by treatment group. Summaries of the number and percentage of patients experiencing a PFS event and the type of event (RECIST 1.1 or death) will be provided along with median PFS for each treatment group.

Sensitivity analyses will be performed to assess possible evaluation-time bias that may be introduced if scans are not performed at the protocol-scheduled time points. The midpoint between the time of progression and the previous evaluable RECIST assessment will be analyzed using a log-rank test. For patients whose death was treated as PFS event, the date of death will be used to derive the PFS time used in the analysis. This approach has been shown to be robust even in highly asymmetric assessment schedules (Sun and Chen 2010).

Attrition bias will be assessed by repeating the PFS analysis except that the actual PFS event times, rather than the censored times, of patients who progressed or died in the absence of progression immediately following 2 or more non-evaluable tumor assessments will be included. In addition, patients who take subsequent therapy prior to progression or death will be censored at their last evaluable assessment prior to taking the subsequent therapy. This analysis will be

supported by a Kaplan-Meier plot of the time to censoring where the censoring indicator of the PFS analysis is reversed.

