3.2 Outcome Variables

All RECIST assessments, whether scheduled or unscheduled, will be included in the calculations. This is also regardless of whether a patient discontinues investigational product.

RECIST 1.1 outcomes (i.e. PFS, ORR etc.) will be derived using the overall visit responses and relevant dates from the BICR. This will be repeated using the programmatically derived overall visit responses from investigator RECIST 1.1 assessments.

Where applicable, in the derivation of endpoints, anti-cancer therapy does not include subsequent radiotherapy.

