3.2.1 Progression-free survival (PFS)

PFS (per RECIST 1.1 as assessed by the BICR) will be defined as the time from the date of randomization until the date of objective disease progression or death (by any cause in the absence of progression) regardless of whether the patient withdraws from randomized therapy or receives another anti-cancer therapy prior to progression (i.e. date of event or censoring – date of randomization + 1). Patients who have not progressed or died at the time of analysis will be censored at the time of the latest date of assessment from their last RECIST 1.1 assessment. However, if the patient progresses or dies after 2 or more consecutive missed visits, the patient will be censored at the time of the latest RECIST 1.1 assessment prior to the 2 missed visits (Note: NE is not considered a missed visit). A 'look-back' approach will be taken (i.e. if an event e.g. progression or death is observed, then it will be considered an event only if there is an assessment within the 2 visit window immediately before the event, irrespective of whether there were missed visits prior to that assessment). If the patient has no evaluable visits or does not have baseline data they will be censored at Day 1 unless they die within 2 visits of baseline i.e. ≤ 119 days (2 x 8 weeks plus 1 week allowing for a late assessment within the visit window), then they will be treated as an event with date of death as the event date.

Given the scheduled visit assessment scheme (i.e. $q8w \pm 1w$ for the first 72 weeks then $q12w \pm 1w$ up to 96 weeks then $q24w \pm 1w$ thereafter) the definition of 2 missed visits will change. See Appendix B for further details on the derivation of the 2 missed visit rule for RECIST assessments.

The PFS time will always be derived based on scan/assessment dates not visit dates.

PFS will also be obtained using the algorithm described above for the RECIST site investigator tumor data.

RECIST 1.1 assessments/scans contributing towards a particular visit may be performed on different dates. The following rules will be applied:

- For BICR assessments, the date of progression will be determined based on the earliest scan dates of the component that triggered the progression for the adjudicated reviewer selecting PD or of the reviewer who read baseline first if there is no adjudication.

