A sensitivity analysis will be performed to assess possible evaluation-time bias that may be introduced if scans are not performed at the protocol-scheduled time points. The midpoint between the time of progression and the previous evaluable RECIST assessment (using the final date of the assessment) will be analyzed using a stratified log-rank test, as described for the primary analysis of PFS. Note that midpoint values resulting in non-integer values should be rounded down. For patients whose death was treated as a PFS event, the date of death will be used to derive the PFS time used in the analysis. This approach has been shown to be robust to even highly asymmetric assessment schedules (Sun and Chen 2010). To support this analysis, the mean of patient-level average inter-assessment times will be tabulated for each treatment group. This approach will use the BICR RECIST assessments.

Attrition bias

Attrition bias will be assessed by repeating the primary PFS analysis except that the actual PFS event times, rather than the censored times, of patients who progressed or died in the

absence of progression immediately following two, or more, non-evaluable tumor assessments will be included. In addition, patients who take subsequent therapy (note radiotherapy is not considered a subsequent anti-cancer therapy) prior to their last RECIST assessment or progression or death will be censored at their last assessment prior to taking the subsequent therapy. This analysis will be supported by a Kaplan-Meier plot of the time to censoring from the primary analysis where the censoring indicator of the PFS analysis is reversed. This approach will use the BICR RECIST assessments.

• Ascertainment bias

Ascertainment bias will be assessed by analyzing the site investigator data. The stratified log rank test will be repeated on the programmatically derived PFS using the site investigator data based upon RECIST. The HR and CI will be presented.

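### The midpoint rule in the evaluation-time sensitivity analysis of PFS has no lower limit at randomization, so progressions found at the first on-study scan can be imputed too early and, in rare cases, at zero or negative times

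*SAP*

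**What the plan says.** SAP 4.2.2, under Evaluation-Time bias, states: "The midpoint between the time of progression and the previous evaluable RECIST assessment (using the final date of the assessment) will be analyzed". The analysis is a stratified log-rank test on BICR assessments. Protocol 9.5.1.1 has the same rule in shorter form: "The midpoint between the time of progression and the previous evaluable RECIST assessment will be analyzed using a log-rank test".

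The SAP adds two details. On rounding: "Note that midpoint values resulting in non-integer values should be rounded down". On deaths: "For patients whose death was treated as a PFS event, the date of death will be used". Neither document gives a lower limit for the imputed date or a rule for progression at the first on-study scan.

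Three other provisions bear on this:

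- **Time origin.** SAP 3.2.1 says PFS "will be defined as the time from the date of randomization until the date of objective disease progression or death", computed as "date of event or censoring – date of randomization + 1".
- **Baseline scan.** SAP 3.1 says: "Baseline radiological tumor assessments are to be performed post-cCRT within the 42 days before randomization and start of study treatment". SAP 2.2 and 3.2.10 treat this scan as a RECIST assessment. SAP 2.2 lists a baseline scan more than 42 days before randomization as an important deviation, but the patient stays in the full analysis set.
- **Unscheduled scans.** SAP 3.2 says: "All RECIST assessments, whether scheduled or unscheduled, will be included in the calculations".

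**The concern.** For a patient whose progression is found at the first on-study scan, the assessment before it is the baseline scan. Half of the interval back to that scan can lie before randomization, when the patient was not yet under observation for PFS. Two patients with identical on-study scans can then receive imputed times up to three weeks apart because their screening scans fell on different days. That is a scan-timing artefact inside an analysis meant to test for scan-timing artefacts.

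If the baseline lag exceeds the time to progression, the imputed time is zero or negative, which the PFS definition does not allow. Whether such a record is kept, set to one day or dropped would then depend on the program rather than the plan. The analysis is prespecified for a dual-primary endpoint, is run for both active arms against placebo, and appears on the forest plot beside the primary result, so the rule should be complete.

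**Working it through.** The documents give no figure for the midpoint rule, so there is none to reproduce. The planning medians used below are consistent: 10 / 0.65 = 15.4 months, the stated 5.4-month gain (SAP 1.3).

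**Formula.** Let progression be found *d* days after randomization and the baseline scan be *b* days before it.

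- As written: imputed PFS = floor((d − b)/2) + 1.
- With randomization as the lower limit: floor(d/2) + 1.

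The first scheduled scan is at 8 weeks ± 1 week, so d = 49 to 63 (SAP 3.1). In window, b is at most 42.

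| Progression day d | b = 1 | b = 14 | b = 28 | b = 42 | Limit at randomization |
|---|---|---|---|---|---|
| 28 (unscheduled) | 14 | 8 | 1 | −6 | 15 |
| 40 (unscheduled) | 20 | 14 | 7 | 0 | 21 |
| 49 (earliest in window) | 25 | 18 | 11 | 4 | 25 |
| 56 (on schedule) | 28 | 22 | 15 | 8 | 29 |

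**Shortening.** It is about b/2, so at most 42/2 = 21 days in window. The mean depends on baseline timing, which the documents do not give:

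- Baseline uniform over 1-42 days before randomization: mean b = 21.5, mean shortening 10.75, about 11 days.
- End of chemoradiotherapy uniform over 1-42 days before randomization, and the scan uniform between that date and randomization: mean b = (21.5 + 1)/2 = 11.25, mean shortening about 5.6 days.

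**Patients affected.** Exponential PFS with a 30.4375-day month:

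- Placebo, median 10 months: 1 − exp(−ln 2 × (56/30.4375)/10) = 12.0%, or 31 of 262.
- Durvalumab, median 15.4 months: 1 − exp(−ln 2 × (56/30.4375)/15.4) = 7.9%, or 21 of 262.
- Total 52 of 524. If 10% of events are deaths (assumed), which keep their own date, about 28 + 19 = 47.

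**Zero or negative times.** These occur exactly when d < b. With both scans in window the smallest value is floor((49 − 42)/2) + 1 = 4 days. A value of zero or less therefore needs an unscheduled progression scan by day 41, or a baseline scan at least 50 days before randomization (d = 49, b = 50 gives 0). Simulated trials of 262 against 262 gave none when every progression was found on schedule. With 25-50% of progressions found on unscheduled scans (assumed), they gave about 2-4 of 524 under the tighter baseline timing above and about 5-9 under uniform 1-42 days.

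**Effect on the comparison.** In simulation with all scans on schedule, the hazard ratio was 0.635 under either rule and the largest change in the log-rank Z was 0.05. Dropping the zero or negative records hardly moved the average hazard ratio, but moved it in individual simulated trials by an amount of the order of 0.01 to 0.02.

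**The case against.** The strongest reply is that SAP 4.2.2 never names the baseline scan. Elsewhere the SAP uses evaluable assessments and visits as if they were post-baseline only: 3.2.9 has a category for patients who die with none, and 3.2.1 lists having no evaluable visits separately from having no baseline data. On that reading the rule does not reach back before randomization; it gives no value at all for these patients. This stands as a real ambiguity. It does not remove the gap, because an undefined time also needs a rule and the same clause supplies it.

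Second, long baseline lags should be uncommon. The scan must follow chemoradiotherapy, which itself ends 1 to 42 days before randomization, and protocol Appendix F asks for the scan as close to randomization as possible. Uniform 1-42 days is therefore near an upper bound, which is why a range is shown.

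Third, a limit at randomization is a convention. No scan is required on that day, so the last imaging evidence of non-progression is the baseline scan. That is fair, but PFS starts at randomization and an event cannot precede its own time origin.

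A reader might also infer more than the documents support:

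- **That a log-rank test cannot use such times.** The test depends only on their order and would rank them first. How software treats negative times is a separate matter on which the plan is silent.
- **That events would be lost, more of them on placebo, or patched after unblinding.** Nothing in the plan says records would be dropped, and protocol 6.2.4 puts decisions on evaluability before unblinding.

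**Conclusion.** The rule is incomplete as written. On its natural reading it imputes first-scan progressions too early, by about half the baseline lag, for roughly 50 of 524 patients under the planning medians. The maximum is 21 days in window; the mean is about 6 to 11 days, depending on assumed baseline timing. Zero or negative times are possible but are a corner case, and their count rests on an assumed share of progressions found off schedule.

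It would be wrong to infer that the sensitivity analysis is materially biased. The rule is the same in both arms, the affected events stay at the start of the time scale, and the expected change in the hazard ratio is under 0.001 unless zero or negative records are dropped. The analysis is supportive, and neither the primary PFS analysis nor any alpha is affected. Severity is minor.

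**What to change.** In SAP 4.2.2, define the lower end of the interval as the later of the randomization date and the last evaluable RECIST assessment before progression, and take the midpoint from there, rounded down as already planned. Make the same change in protocol 9.5.1.1 or, until it is next amended, record it in SAP Section 6.

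Every imputed time is then at least 1 day. An on-schedule week 8 progression gets 29 days whatever the baseline date, and the rule is defined under either reading of the previous evaluable assessment. The cost is one clause and one line of code, best settled before the data are unblinded.
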